**8.1.1 Required Observations Following Completion of Protocol Therapy**

The following studies are required until the patient is off study as defined in [Section 10.2](#).

STUDIES TO BE OBTAINED	~100 Days After Last dose of Nivolumab	Every 6 months up to 24 Months	Annually up to 60 Months
History	X	X	X
Physical exam with vital signs	X	X	X
CBC, differential, platelets	X	X	X
Tumor disease evaluation	X	X	X
Treatment with stem cell transplant	X	X	X
Evidence of or history of GVHD	X	X	X

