Nivolumab (1 mg/kg) in combination with ipilimumab (3 mg/kg) has been FDA approved for adults with BRAF wild-type melanoma. Approval was based on data from CheckMate 069 trial which randomized patients with previously untreated, unresectable stage III or IV melanoma to receive nivolumab (1 mg/kg) plus ipilimumab (3 mg/kg) vs. ipilimumab (3 mg/kg) plus placebo. Patients treated on the nivolumab plus ipilimumab received the combination every 3 weeks x 4 doses then received nivolumab single agent 3 mg/kg every 2 weeks. Treatment-related grade 3-4 adverse events were reported in 51 (54%) of 94 patients who received nivolumab plus ipilimumab compared with nine (20%) of 46 patients who received ipilimumab alone. The most common treatment-related grade 3-4 adverse events were colitis (12 [13%] of 94 patients) and increased alanine aminotransferase (ten [11%]) in the combination group and diarrhea (five [11%] of 46 patients) and hypophysitis (two [4%]) in the ipilimumab alone group. Serious grade 3-4 treatment-related adverse events were reported in 34 (36%) of 94 patients who received nivolumab plus ipilimumab (including colitis in ten [11%] of 94 patients, and diarrhea in five [5%]) compared with four (9%) of 46 patients who received ipilimumab alone (including diarrhea in two [4%] of 46 patients, colitis in one [2%], and hypophysitis in one [2%]) The 2-year overall survival was 63.8% (95% CI 53.3% (.6) for those assigned to nivolumab plus ipilimumab and 53.6% (95% CI 38.1% (.8) for those assigned to ipilimumab alone.

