*Patients with purpuric or bullous lesions must be evaluated for vasculitis, Steven-Johnson syndrome, TEN, and autoimmune bullous disease including oral lesions of bullous pemphigus/pemphagoid. Pruritus may occur with or without skin rash and should be treated symptomatically if there is no associated liver or GI toxicity. Note skin rash typically occurs early and may be followed by additional events particularly during steroids tapering.	
Recommended management: See Skin AE Management Algorithm	

6.4.1 **BMS Recommended Skin Adverse Management Algorithm**

These suggested management guidelines are taken from the BMS algorithms provided in the Investigator's Brochure.

Toxicity (CTCAE v.5)	Management	Follow-up
Grade 1/2 Rash	
 
• Symptomatic therapy (e.g. antihistamines, topical steroids)
 
• Continue protocol therapy
 
	
If persists > 1-2 weeks or recurs:
 
 
• Consider skin biopsy
 
• Hold protocol therapy
 
• Consider 0.5-1 mg/kg/day methylprednisolone IV or oral equivalent
 
• Once improving, taper steroids over at least 1 month
 
• Consider prophylactic antibiotics for opportunistic infections
 
 
If worsens: Treat as Grade 3/4

Grade 3/4 Rash	
 
• Hold infusion
 
• Consider skin biopsy
 
• Dermatology consult
 
• 0.5-1 mg/kg/day methylprednisolone IV or IV equivalent
 
	
If improves to Grade 1:
 
 
• Taper steroids over at least 1 month,
 
• Add prophylactic antibiotics for opportunistic infections
 

Patients on IV steroids may be switched to an equivalent dose of oral corticosteroids (e.g. prednisone) at start of tapering or earlier, once sustained clinical improvement is observed. Lower bioavailability of oral corticosteroids should be taken into account when switching to the equivalent dose of oral corticosteroids.

6.5 **Dose modifications for Hepatic/Pancreatic Adverse Events**

Liver Function Elevation	Management/Next Dose of Nivolumab ± Ipilimumab
≤ Grade 1	Continue protocol therapy
Grade 2	Hold until baseline. If resolves within 7 days, resume at same

Liver Function Elevation	Management/Next Dose of Nivolumab ± Ipilimumab
	dose level.

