## 8.0 EVALUATIONS/MATERIAL AND DATA TO BE ACCESSIONED

### 8.1 Required Clinical, Laboratory and Disease Evaluation

All clinical and laboratory studies to determine eligibility must be performed within 7 days prior to enrollment unless otherwise indicated. Laboratory values used to assess eligibility (see [Section 4.0](#)) must be no older than seven (7) days at the start of therapy. Laboratory tests need **not** be repeated if therapy starts **within** seven (7) days of obtaining labs to assess eligibility. If a post-enrollment lab value is outside the limits of eligibility, or laboratory values are older than 7 days, then the following laboratory evaluations must be re-checked within 48 hours prior to initiating therapy: CBC with differential, bilirubin, ALT (SGPT) and serum creatinine. If the recheck is outside the limits of eligibility, the patient may not receive protocol therapy and will be considered off protocol therapy. Imaging studies must be obtained within 14 days prior to start of protocol therapy (repeat the tumor imaging if necessary).

STUDIES TO BE OBTAINED	Pre-Study	During Cycle 1	Prior to Subsequent Cycles ^
History	X	Weekly	X
Physical Exam with vital signs	X	Weekly	X
Height, weight, BSA	X		X
Performance Status	X		X
Pregnancy Test 	X		
CBC, differential, platelets	X	Weekly 	Weekly 
Urinalysis	X		X
Electrolytes including Ca ++ , Cl, PO 4 , Mg ++	X	Weekly	X
Creatinine, ALT*, AST*, bilirubin	X	Weekly	X
Amylase, lipase, CRP	X		X
TSH 	X	End of Cycle 1	X
Tumor Disease Evaluation- Parts A and B	X	End of Cycle 1	End of cycle 2, then q 3 cycles 
Tumor Disease Evaluation- Parts C, D, and E	X	End of Cycle 2	End of cycle 4, then q 3 cycles 
Pulse Oximetry	X		With Tumor Disease Evaluation
Pharmacokinetics  (Required)	X	X 	X
Vaccine Antibody and Cytokine Studies  (Optional)	X	X	X
Anti-Drug Antibody (ADA)  (Required)	X	X	X
Tumor Tissue (Required, if available)	X 		X 
EKG  , ECHO 	X	Clinically Indicated	
CPK and Troponin 	X	Clinically Indicated	

^ Studies may be obtained within 72 hours prior to the start of the subsequent cycle.

\* For the purpose of this study, the ULN for SGOT (AST) is 50 U/L and the ULN for SGPT (ALT) is 45 U/L.

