## 10.0 **CRITERIA FOR REMOVAL FROM PROTOCOL THERAPY AND OFF STUDY CRITERIA**

### 10.1 **Criteria for Removal from Protocol Therapy**

- a) Clinical (including physical examination or serum tumor markers) or radiographic evidence of progressive disease of greater than 40% increase from baseline target lesions selected according to RECIST criteria (See [Section 12.0](#)).
- b) Clinical (including physical examination or serum tumor markers) or radiographic evidence of progressive disease > 12 weeks after start of protocol therapy.
- c) Adverse Events requiring removal from protocol therapy (See [Sections 5.4](#) and [6.0](#)).
- d) Immune adverse events requiring removal from protocol therapy (See [Section 5.4](#)

- and [Section 6.0](#)) which in the opinion of the treating physician are consistent with acute or chronic GVHD requiring systemic immunosuppression.
- e) Refusal of further protocol therapy by patient/parent/guardian
  - f) Non-compliance that in the opinion of the investigator does not allow for ongoing participation.
  - g) Physician determines it is not in the patient's best interest.
  - h) Repeated eligibility laboratory studies (CBC with differential, bilirubin, ALT (SGPT) or serum creatinine) are outside the parameters required for eligibility prior to the start of protocol therapy (See [Section 8.1](#)).
  - i) Study is terminated by Sponsor.
  - j) Pregnancy

**Patients who are removed from protocol therapy during cycle 1 (Part A and B) or during cycles 1 and 2 (Parts C, D, or E) should continue to have the required observations in [Section 8.1](#) until the originally planned end of the cycle or until all adverse events have resolved per [Section 13.4.4](#), whichever happens LATER. The only exception is with documentation of the patient's withdrawal of consent. Patients who are removed from protocol therapy in subsequent cycles should have the necessary observations to ensure adequate clinical care.**

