Patients who are off protocol therapy are to be followed as described in [Section 8.1.1](#) until they meet the criteria for Off Study (see below). Ongoing adverse events, or adverse events that emerge after the patient is removed from protocol therapy, but within 100 days of the last dose of investigational agent, must be followed and reported via RAVE and CTEP-AERS (if applicable). Serious adverse events that occur during the follow-up period (more than 30 days after the last administration of investigational agent) and have an attribution of possible, probable, or definite require reporting per [Footnote 1](#) of Table A. Follow-up data will be required unless consent is withdrawn.

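### After a last dose in Cycle 3 or later of Parts C–E (or after Cycle 1 of Parts A/B), no chemistry, lipase or TSH is scheduled, so late laboratory toxicity is not systematically sought

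*Combined protocol and SAP*

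**What the plan says.** **On treatment (Section 8.1 table).** Creatinine, ALT, AST and bilirubin are required at baseline and weekly in Cycle 1. TSH is required at baseline and at the end of Cycle 1. Amylase and lipase are required at baseline, with no Cycle 1 entry. After Cycle 1 all of these appear only under "Prior to Subsequent Cycles", which a footnote places in the 72 hours before the next cycle starts. The blood count alone stays weekly.

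**Early removal (Section 10.1).** Patients removed in Cycle 1 (Parts A/B) or in Cycles 1 and 2 (Parts C–E) "should continue to have the required observations in" Section 8.1 to the planned cycle end or until adverse events resolve, whichever is later. For later removals the section asks only for what adequate clinical care needs, and names no test or time.

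**After therapy (Section 8.1.1).** The table is introduced with "The following studies are required until the patient is off study as defined in" Section 10.2. Its first column is headed "100 Days After Last dose of Nivolumab". It lists history, physical exam, tumor evaluation, transplant and GVHD items, and one laboratory row: "CBC, differential, platelets".

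**Reporting window.** Section 10.1 requires adverse events that emerge within 100 days of the last dose to be followed and reported. Section 10.2 takes Part E patients off study at 100 days, so the 100-day visit is their only scheduled post-therapy visit.

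**The concern.** The period over which adverse events are collected is longer than the period over which the tests that reveal silent ones are scheduled. A rise in ALT, creatinine or lipase, or a failing thyroid, can occur without symptoms, and history and examination will not reliably show it.

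The protocol itself expects such events late. Section 2.4 reports immune-related events in the pediatric ipilimumab trial up to week 36, though most came in the first three weeks. The ipilimumab risk list in Section 9.2.8 notes a minority of reactions weeks to months after stopping. Section 6.5 warns that liver tests can change during steroid tapers given for other events. Section 6.6 takes Part C–E patients off therapy for any Grade 2 diarrhea or colitis, and the algorithm in 6.6.1 describes steroid tapers of at least a month, which would fall in the period with no scheduled chemistry.

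Describing the toxicities of the combination is a primary aim (Section 1.1), and Section 5.4 relies on careful monitoring of delayed toxicity. If post-dose testing follows local habit, the late-toxicity profile depends partly on where patients were treated.

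**Working it through.** The plan gives no figure to reproduce here. The check sets the schedules side by side and counts days.

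**Inputs**
- Parts C–E: Cycles 1–4 last 21 days with dosing on Day 1; Cycles 5+ last 28 days with dosing on Days 1 and 15 (Section 5.1).
- Parts A/B: 28-day cycles with dosing on Days 1 and 15 (Section 5.1).
- Pre-cycle panel: drawn 0 to 3 days before the cycle starts (Table 8.1 footnote).
- Adverse-event window: 100 days after the last dose (Section 10.1).

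**Formulas**
- Age of the last panel at the last dose = (day of last dose − 1) + 0 to 3 days.
- Days of the window without a scheduled panel = 100 − days after the last dose through which testing is required.

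**Results for ALT and creatinine, with no adverse event open at cycle end**

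| Last dose | Last scheduled test | Days without |
|---|---|---|
| Parts C–E, Cycle 1 | Weekly to cycle end | 100 − 21 = 79 |
| Parts C–E, Cycle 2, if the extension includes the panel | Cycle end | 100 − 21 = 79 |
| Parts C–E, Cycle 2, if the extension adds only the blood count | 0–3 days before the dose | 100 |
| Parts C–E, Cycle 3 or 4 | 0–3 days before the dose | 100 |
| Parts C–E, Cycle 5+, Day 15 | 14 + (0 to 3) = 14–17 days before the dose | 100 |
| Parts A/B, Cycle 1, Day 1 | Weekly to cycle end | 100 − 28 = 72 |
| Parts A/B, Cycle 1, Day 15 | Weekly to cycle end, about 14 days | 100 − 14 = 86 |
| Parts A/B after Cycle 1, Day 15 | 14–17 days before the dose | 100 |

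The visit at about 100 days does not end the interval, because it has no chemistry row.

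**TSH** matches the table for removals after Cycle 1. For Cycle 1 removals it is drawn once, at cycle end.

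**Lipase** is weaker still. Table 8.1 has no Cycle 1 entry, so the Section 10.1 extension has nothing to continue. For a Cycle 1 removal the last scheduled lipase is the baseline one.

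**Why Cycle 2 is ambiguous.** Between the starts of Cycles 2 and 3 the only laboratory test with its own timing is the weekly blood count. On the other side, the panel drawn within 72 hours of the next cycle would fall at the end of Cycle 2, and the same column also holds an end-of-cycle tumor evaluation. Both readings are possible.

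**Context on frequency.** For the adult trial of the Part E doses, Section 2.3 reports "increased alanine aminotransferase (ten [11%]) in the combination group", that is 10/94 = 10.6% Grade 3–4. If that rate applied, 20 × 0.106 = 2.1 of 20 Part E patients would have such an event at some time (20 × 0.05 = 1 at a 5% rate; 20 × 0.20 = 4 at 20%). At the expected size of 14 that Section 11.7.1 gives for a true response rate of 5%, it is 14 × 0.106 = 1.5. These are any-time figures. They show that the event type is not rare, not how many fall after the last dose.

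**The case against.** The other side has several good points.

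- **Early removals are covered in part.** A reader might infer that no organ-function test is ever required after a last dose. Section 10.1 rules that out: Cycle 1 removals keep weekly ALT and creatinine and the end-of-cycle TSH.
- **Events are not simply lost.** It is tempting to say that late toxicity is missed. The documents require emerging events to be followed and reported for 100 days, ask for clinically adequate observation of later removals, schedule history and examination, and give hepatic and renal algorithms (6.5.1, 6.13.1) that call for monitoring after discontinuation. That stands, but the algorithms start from a known abnormality and the rest names no test. Detection is unscheduled, not absent.
- **The blood count has a purpose.** One might infer that the late risks are all non-hematologic. The Section 9.2.8 note on post-discontinuation reactions also lists hemolytic anemia, red cell aplasia and an anti-factor VIII response. The count is worth keeping; it is just not sufficient.
- **Most immune events are early.** In the pediatric ipilimumab trial most fell in the first three weeks, when ALT and creatinine are weekly. This limits the size of the gap but does not remove it.
- **Day 15 in Cycles 5+.** A reader might see a contradiction between one panel per 28 days and the Section 6.5 column "Management/Next Dose of Nivolumab ± Ipilimumab". The documents do not support that: Section 6.5 says what follows from a given grade, and its algorithm refers back to routine monitoring per Table 8.1. At most the sponsor could confirm that the two are consistent.

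**Conclusion.** The point holds in limited form. For last doses in Cycle 3 or later of Parts C–E, and after Cycle 1 of Parts A/B, no creatinine, ALT, AST, bilirubin, lipase or TSH is scheduled anywhere in the 100-day reporting window. When the last dose is a Day 15 dose, the latest scheduled panel is already 14–17 days old. For Cycle 2 removals in Parts C–E the text can be read either way. For Cycle 1 removals only lipase lacks any scheduled test after the dose.

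The consequence is uneven ascertainment: Part E's descriptive late-toxicity profile may be biased low and may differ between sites. The Part E toxicity stopping rule counts Cycle 1 dose-limiting toxicity, when ALT and creatinine are weekly, so it is not affected.

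The day counts assume no open adverse event and no testing beyond the schedule. The documents give no rate of laboratory toxicity after the last dose, so the number of undetected events cannot be stated, and the adult 11% should not be read as that number.

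**What to change.** 1. In Table 8.1.1, add creatinine, ALT, AST, bilirubin, lipase and TSH to the column for about 100 days after the last dose, at the blood draw already made for the blood count.
2. In Table 8.1 and Section 10.1, state that the pre-cycle panel is also due at the end of the last cycle received when no further cycle starts. This settles the Cycle 2 ambiguity and gives Cycle 1 removals a lipase.

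Parts A–D are marked completed in Section 5.1, so the practical benefit is for Part E.

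The cost is an amendment to two tables and one paragraph, a small extra blood volume, and a routine panel. For some patients the end-of-cycle draw would be additional: one who stops in Cycle 3, for example, has no tumor evaluation scheduled at that cycle's end. No change to Day 15 testing is proposed.

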**8.2 Radiology Studies**

Central Radiology Review for Response:

Patients who respond (CR, PR) to therapy, have pseudoprogression or have long term stable disease (SD) (≥ 6 cycles) on protocol therapy will be centrally reviewed. The response of MIBG lesions will also be assessed by central review (See [Section 12.4](#)). COG Operations Center will notify the Imaging Center of any patient requiring central review. The Imaging Center will then request that the

treating institution forward the requested images for central review. The central image evaluation results will be entered into RAVE for review by the COG Operations Center and for data analysis.

The images are to be forwarded electronically to the Imaging Research Center at Children's Hospital Los Angeles via the ImageInBox.

COG institutions that are not connected via the ImageInBox can send the images on hard copy film, CD ROM, USB flash drive or by FTP. Submitted imaging studies should be clearly marked with the COG patient ID, study number (ADV1412) and date and shipped to [name] at the address below:

[name], CRP  
Administrator, Imaging Research Center  
Children's Hospital Los Angeles  
[name]  
[name]  
[contact]  
[contact]

### 8.3 Pharmacokinetics (Required)

#### 8.3.1 Analysis

Serum samples will be collected for pharmacokinetic evaluation of nivolumab and/or ipilimumab by validated immunoassay by PPD - Pharmaceutical Product Development, LLC. PK parameters will include Cmax, Cmin, Tmax, AUC(TAU) and AUC(0-21).

#### 8.3.2 Sampling Schedule

Blood samples will be obtained prior to drug administration and as outlined in [Appendix IIIA](#) for Parts A and B, and [Appendix IIIB](#) for Parts C, D, and E.

#### 8.3.3 Sample Collection and Handling Instructions

Blood samples (2 ml for parts A and B and 2 x 2ml for parts C, D, and E) will be collected in SST Vacutainer tubes at a site distant from the infusion for pharmacokinetic evaluation. Samples cannot be drawn from the 2nd lumen of a multi-lumen catheter through which drug is being administered. Record the exact time that the sample is drawn along with the exact time that the drug is administered (including drug start and stop times).

1. For timepoints where both PK and ADA samples are collected, an 8.5mL SST tube is used.

2. For timepoints where only a PK sample is collected, the 4mL SST tube is used.

#### 8.3.4 Sample Processing Instructions:

1. Immediately after collection, gently invert each blood sample 5-10 times and allow blood to clot for 30-45 minutes at room temperature (tube standing upright).

2. Centrifuge samples at room temperature for 10 minutes (swing out) or 15 minutes (fixed) at 1100-1300 x g until clot and serum are well separated.

3. Aliquot according to the following:

a. PK-only timepoints- transfer all serum into one appropriately

- labeled 2 mL screw-capped polypropylene tube
  - b. PK and ADA- transfer serum equally into two appropriately labeled 3 mL screw-capped polypropylene tubes
4. Store the serum samples immediately (within 1 hour of collection) at approximately -20°C or -70°C (preferred) until they are shipped on dry ice to the address in [Section 8.3.6](#).

#### 8.3.5 Sample Labeling

Each tube must be labeled with the patient's study registration number, the study I.D., and the date and time the sample was drawn. Data should be recorded on the Pharmacokinetic Study Form, which must accompany the sample(s).

### 8.4 **Vaccinated Antibody Studies (optional)**

#### 8.4.1 Analysis

In consenting patients, PD analysis will be done by Covance on serum samples for retrospective analysis of changes in antibody titers to previously vaccinated antigens following treatment with nivolumab alone and in combination with ipilimumab.

#### 8.4.2 Sampling Schedule

Blood samples will be obtained prior to drug administration and as outlined in [Appendix IV](#).

#### 8.4.3 Sample Collection and Handling Instructions

Blood samples (2 ml) will be collected in 4 mL SST Vacutainer tubes at a site distant from the infusion. Samples cannot be drawn from the 2nd lumen of a multi-lumen catheter through which drug is being administered. Record the exact time that the sample is drawn along with the exact time that the drug is administered (including drug start and stop times).

#### 8.4.4 Sample Processing and Shipping Instructions:

1. Immediately after collection, gently invert each blood sample 5-10 times and allow blood to clot for 30-45 minutes at room temperature (tube standing upright).
2. Centrifuge samples at room temperature for 10 minutes (swing out) or 15

- minutes (fixed) at 1100-1300 x g until clot and serum are well separated.
3. Transfer all serum into one appropriately labeled 2 mL screw-capped polypropylene tube
  4. Store the serum samples immediately (within 1 hour of collection) at approximately -20°C or -70°C (preferred) until shipment.

Refer to the guidelines provided for sample shipping instructions.

#### 8.4.6 Sample Labeling

Each tube must be labeled with the patient's study registration number, the study I.D., and the date and time the sample was drawn. Data should be recorded on the Vaccinated Antibody Study Form, which must accompany the sample(s).

### 8.5 **Anti-drug antibody (ADA) analysis (Required)**

Analysis: ADA analysis will be done by PPD - Pharmaceutical Product Development, LLC using an ELISA assay.

#### 8.5.1 Sampling Schedule

Blood samples will be obtained as outlined in [Appendix V](#).

#### 8.5.2 Sample Collection and Handling Instructions

Blood samples (2 ml) will be collected in SST Vacutainer tubes at a site distant from the infusion. Samples cannot be drawn from the 2nd lumen of a multi-lumen catheter through which drug is being administered. Record the exact time that the sample is drawn along with the exact time that the drug is administered (including drug start and stop times).

1. For timepoints where both PK and ADA samples are collected, an 8.5 mL SST tube is used.
2. For timepoints where only an ADA sample is collected, the 4 mL SST tube is used.

